7 PARAMETERS AND METHODS OF ASSESSMENT

7.1 Safety Parameters

7.1.1 Adverse Events

7.1.1.1 Definitions

Pre-treatment Event (PTE)

A PTE is defined as any untoward medical occurrence in a clinical investigation subject who has signed informed consent to participate in a study but prior to administration of any study medication; it does not necessarily have to have a causal relationship with study participation.

Adverse Event (AE)

An AE is any untoward medical event that occurs in a subject who has received study medication and does not necessarily have a causal relationship with study treatment. An AE can therefore be any unfavorable and unintended sign (including an abnormal laboratory finding), symptom, or disease temporally associated with the use of an investigational product, whether or not related to the product.

A treatment-emergent AE will be defined as an AE that begins or that worsens in severity after the first dose of study drug has been administered.

An adverse drug reaction (ADR) is any untoward and unintended response in a subject to an IMP which is related to any dose administered to that subject.

An unexpected adverse reaction is an adverse reaction the nature and severity of which is not consistent with the information about the medicinal product in the Investigator's Brochure.

All PTEs/AEs, including intercurrent illnesses, occurring during the study will be documented in the eCRF.

Each event should be recorded to represent a single diagnosis. Accompanying signs (including abnormal laboratory values or ECG findings) or symptoms should NOT be recorded as additional AEs. If a diagnosis is unknown, sign(s) or symptom(s) should be recorded appropriately as a PTE(s) or as an AE(s).

7.1.1.2 Laboratory values and ECG findings

Changes in laboratory values or ECG parameters are only considered to be PTEs or AEs if they are judged to be clinically significant (i.e., if some action or intervention is required or if the Investigator judges the change to be beyond the range of normal physiologic fluctuation). A laboratory re-test and/or continued monitoring of an abnormal value are not considered an intervention. In addition, repeated or additional noninvasive testing for verification, evaluation or monitoring of an abnormality is not considered an intervention.

If abnormal laboratory values or ECG findings are the result of pathology for which there is an overall diagnosis (e.g., increased creatinine in renal failure), the diagnosis only should be reported appropriately as a PTE or as an AE.

7.1.1.3 Pre-existing conditions

Pre-existing conditions (present at the time of signing of informed consent) are considered concurrent medical conditions and should NOT be recorded as PTEs. Baseline evaluations (e.g., laboratory tests, ECG, X-rays etc.) should NOT be

recorded as PTEs. However, if the subject experiences a worsening or complication of such a concurrent condition, the worsening or complication should be recorded appropriately as a PTE/AE. Investigators should ensure that the event term recorded captures the change in the condition (e.g., “worsening of...”).

If a subject has a pre-existing episodic condition (e.g., asthma, epilepsy) any occurrence of an episode should only be captured as a PTE/AE if the episodes become more frequent, serious or severe in nature, that is, Investigators should ensure that the AE term recorded captures the change in the condition from Baseline (e.g., “worsening of...”).

If a subject has a degenerative concurrent condition (e.g., cataracts, arthritis), worsening of the condition should only be captured as a PTE/AE if occurring to a greater extent to that which would be expected. Again, Investigators should ensure that the AE term recorded captures the change in the condition from Baseline (e.g., “worsening of...”).

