A single-species finding of cataract was observed in a high dose 6-month rat chronic toxicology study. Importantly, no cataracts were observed in any other toxicology studies, including in a 3-month rat study and a 12-month primate study. It is anticipated that the changes observed in the 6-month rat study are rat strain specific. Nevertheless, following this observation, taking a conservative approach, ophthalmology examinations were included in all REN001 trials. Slit lamp eye examinations will be conducted together with assessments of best corrected visual acuity at Screening and Weeks 12 and 24 in this study.

Potential Drug-Drug Interactions

REN001 is not a direct or time-dependent inhibitor of CYP3A4. However, REN001 has been shown to be a weak inducer of CYP3A4 *in vitro*. A potential for drug interactions between REN001 and drugs that are metabolized through the CYP3A4 is considered low but cannot be ruled out. Therefore, drugs that are metabolized primarily by CYP3A4 and have a narrow therapeutic index should be administered with caution in subjects participating in REN001 studies.

REN001 was identified as a P-glycoprotein (P-gp) substrate *in vitro*. Strong P-gp inhibitors may have an impact on the absorption and metabolism of a P-gp substrate, however preliminary human metabolism for REN001 indicates numerous metabolic pathways are involved in the clearance of REN001. Therefore, it is unlikely that co-administration of a strong P-gp inhibitor with REN001 will result in higher systemic exposures of REN001. Co-administration of REN001 with a strong P-gp inducer may reduce REN001 plasma concentrations.

Fertility and Contraception

In accordance with the latest European regulatory discussions and guidelines ([Clinical Trials Facilitation Group, 2014](#) and [2020](#)), WOCBP are eligible for the study provided they are using a highly effective form of contraception from Screening, while taking the study drug and for 30 days after stopping study drug (at least one menstrual cycle after drug exposure). Serum pregnancy testing will be completed at Screening and urine pregnancy tests will be carried out monthly thereafter and at Follow Up.

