7.1.1.5 Adverse Events of Special Interest

Adverse events of special interest are those of scientific and medical concern specific to the Sponsor’s product for which ongoing monitoring and rapid communication by the Investigator to the Sponsor may be warranted. These events require further investigation in order to characterize and understand them. Based on this assessment, the Sponsor plans to include events of special interest as follows:

- Changes in laboratory parameters of muscle injury associated with clinically significant adverse events
- Changes observed after Baseline in formation or exacerbation of cataracts or, visual acuity. A spherical equivalent change of ≥ 0.75 diopters will be considered to be a clinically significant change regardless of changes in lens clarity.
- Occurrence of fractures after Baseline.

While AESIs may not meet the definition of an SAE, they should be reported in the same manner as SAEs (See [Section 7.1.1.9](#)). This allows them to be tracked in more detail and followed up for additional information if required. When completing the SAE form there is an extra box to check to confirm that the event is an AESI. AESIs will not be reported to the Regulatory Authorities unless they are also SUSARs.

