6. SAFETY ASSESSMENTS

6.1. ADVERSE EVENT

The incidence, causality and severity of treatment-emergent adverse events (TEAEs), including treatment-emergent serious adverse events (TESAEs) and adverse events of special interest (AESI), will be investigated.

AESI are those of scientific and medical concern specific to mavodelpar and include:

- Changes in laboratory parameters of muscle injury associated with clinically significant adverse events (AEs)
- Changes observed after baseline in formation or exacerbation of cataracts or, visual acuity. A spherical equivalent change of ≥ 0.75 diopters will be considered to be a clinically significant change regardless of changes in lens clarity.
- Occurrence of fractures after baseline

AESI will be identified on the eCRF and will be reported in the same way as serious adverse events (SAEs).

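### The protocol and SAP give three different rules for recording progression of an existing cataract, so the AESI count for that event can be incomplete and uneven across sites

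*Protocol*

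**What the plan says.** Protocol Section 1.4 lists cataract formation among the risks of REN001, because "A single-species finding of cataract was observed in a high dose 6-month rat chronic toxicology study", and gives that finding as the reason for eye examinations in all REN001 trials.

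Three places then say when a lens change becomes a recorded event:

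- **Protocol 7.1.1.3 (pre-existing conditions).** The general rule is that "if the subject experiences a worsening or complication of such a concurrent condition, the worsening or complication should be recorded appropriately as a PTE/AE". A later paragraph narrows it: for a "degenerative concurrent condition (e.g., cataracts, arthritis), worsening of the condition should only be captured as a PTE/AE if occurring to a greater extent" than would be expected. Cataracts are the first example given.
- **Protocol 7.1.1.5 (AESIs).** The list includes "Changes observed after Baseline in formation or exacerbation of cataracts or, visual acuity". It adds that "A spherical equivalent change of ≥ 0.75 diopters will be considered to be a clinically significant change regardless of changes in lens clarity". Of AESIs in general it says "they should be reported in the same manner as SAEs".
- **SAP 6.7 (eye examinations).** An abnormality becomes an AE when it is judged clinically significant.

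On the analysis side, SAP 6.1 repeats the AESI definition and states that "AESI will be identified on the eCRF and will be reported in the same way as serious adverse events". SAP 12.1 tabulates AESIs from those records. Separately, SAP 12.7 summarizes LOCS III lens grades and their change from baseline.

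**The concern.** One event, progression of a cataract that a subject already had at consent, can be handled in opposite ways. Under 7.1.1.3 an investigator who regards the progression as expected records nothing. Under 7.1.1.5 the same event is an AESI that travels by the SAE route, for which Section 7.1.1.9 sets 24 hours. Under SAP 6.7 the test is clinical significance, which is neither of these.

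The event belongs to a risk that the sponsor itself singles out. Because the AESI table is built from what sites enter in the eCRF, an event withheld at the site cannot appear in it. With at least 35 centers, different readings of the same text would also make the count uneven.

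**Working it through.** There is no planned figure to reproduce, and no sample size, power or alpha calculation is involved. The check is a comparison of the texts.

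1. **Do the rules meet on the same event?** Yes, on one only: worsening after Baseline of a cataract present at consent. Section 7.1.1.3 filters it ("worsening of the condition should only be captured as a PTE/AE if occurring to a greater extent to that which would be expected"); Section 7.1.1.5 lists exacerbation without that condition.
2. **Can such subjects be enrolled?** Yes. The only exclusion that names cataract, number 26 in Section 4.2, concerns suitability for cataract surgery. Having a cataract is not an exclusion.
3. **Is there an order of precedence?** None is stated in either protocol section or in the SAP.
4. **Are the terms defined?** Expected progression has no grade change or time frame attached. Exacerbation has no lens-grade threshold either. The one numeric criterion, 0.75 diopters, measures refraction and not opacity.
5. **Does an omission reach the analysis?** Yes. An AESI is an adverse event by definition, and SAP 6.1 identifies it from the eCRF. No step in the SAP adds AESIs from the lens grades.
6. **What is outside the conflict?** A new cataract is not a pre-existing condition, so 7.1.1.3 does not filter it. A spherical equivalent change of at least 0.75 diopters is an AESI whatever the lens shows. Visual acuity is not mentioned in 7.1.1.3.
7. **What else measures the lens?** LOCS III grading at Screening, Week 12, Week 24 and Early Termination (Protocol 7.1.9 and Table 2). SAP 12.7 summarizes four gradings by visit, over both eyes and for the worst change, and SAP 8.2 splits summary tables by treatment group.
8. **How complete is that second view?** SAP 6.7 states that 30 randomized subjects were graded at screening on a system that cannot be converted. They get no change from baseline; their data are listed and reviewed medically. Against the planned 200 randomized, 30 / 200 = 15%. Protocol 8.6 also planned a categorical shift table for eye parameters, whereas SAP 12.7 describes descriptive statistics only, in which worsening in a few subjects is less visible.

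**Direction of the effect.** Let p1 and p0 be the true exacerbation proportions on drug and placebo, and f the fraction left unrecorded as expected, assumed equal in the two arms. The recorded difference is (1 − f)p1 − (1 − f)p0 = (1 − f)(p1 − p0), so the absolute difference shrinks by the fraction f. The ratio is p1/p0, unchanged, but it rests on fewer events. The documents give none of p1, p0, f or the number of subjects with cataract at baseline, so no size can be attached.

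**The case against.** The strongest answer is that the specific rule governs the general one. Section 7.1.1.5 is written for this product, comes two subsections later, and has its own route, including an AESI box on the SAE form. Many sites would read it that way. The reading is plausible, but it is stated nowhere, and 7.1.1.3 names cataracts expressly.

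The second answer is that cataract detection does not depend on AE reporting. Eye assessments are a safety endpoint in their own right, qualified professionals grade every lens, the grades are summarized by arm, and the Safety Review Committee sees unblinded safety data. This stands, with the limits in steps 7 and 8. A reader might infer from the conflict that a cataract signal would be hidden, or that the eye risk as a whole is under-counted. The documents do not support either: the lens data are collected and analyzed whether or not an AE is recorded, and new cataracts are outside the filter.

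Third, the investigator has serial LOCS III grades to judge by, and an excess caused by the drug is more likely to exceed expected progression and so be kept. Blinding also makes different recording by arm less likely. These points are fair and limit the likely bias. They do not give sites a common criterion.

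Finally, making every lens change reportable would send trivial grade fluctuation through SAE-style reporting. That is right, and it is why a defined grade change belongs in the fix.

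**Conclusion.** The inconsistency is real and limited. The AESI count for progression of cataracts present at consent can be incomplete and can differ between sites, because three recording standards coexist with no stated precedence. The AESI tables inherit whatever sites enter.

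The size cannot be computed, since neither baseline cataract prevalence nor a progression rate is given. The direction rests on the assumption that some sites follow 7.1.1.3; the documents allow that but do not show that it happened. It would go too far to say that a site must record nothing, or that any particular halving or loss of a between-arm difference follows; no event rates in the documents support such a figure. The LOCS III summaries remain a separate arm-level check for about 85% of the planned subjects (170 of 200), with listings and medical review for the other 30.

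**What to change.** 1. In Protocol 7.1.1.3, delete cataracts from the examples of degenerative conditions and state that 7.1.1.5 governs cataract formation or exacerbation after Baseline. Issue this as an amendment or a site clarification.
2. Align the AE sentence in SAP 6.7 with that rule.
3. Have the sponsor state, before unblinding, which recorded LOCS III change counts as exacerbation, so that sites and data management apply one criterion and minor grade fluctuation is not reported.
4. Before database lock, query every subject whose LOCS III record meets that criterion and who has no AESI. For the 30 subjects with unconvertible screening grades, use the planned medical review for the same question.

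No change is needed for visual acuity, where 7.1.1.3 contains no conflicting text. If most visits are already complete, step 4 matters most, because the grades exist and missed events can still be recovered. The cost is a few sentences of text, some additional AESI reports and one query run.

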7.1.1.4 Worsening of PTEs or AEs

If the subject experiences a worsening or complication of a PTE after starting administration of the study medication, the worsening or complication should be recorded appropriately as an AE. Investigators should ensure that the AE term recorded captures the change in the condition (e.g., “worsening of...”).

If the subject experiences a worsening or complication of an AE after any change in study medication, the worsening or complication should be recorded as a new AE. Investigators should ensure that the AE term recorded captures the change in the condition (e.g., “worsening of...”).

7.1.1.5 Adverse Events of Special Interest

Adverse events of special interest are those of scientific and medical concern specific to the Sponsor’s product for which ongoing monitoring and rapid communication by the Investigator to the Sponsor may be warranted. These events require further investigation in order to characterize and understand them. Based on this assessment, the Sponsor plans to include events of special interest as follows:

- Changes in laboratory parameters of muscle injury associated with clinically significant adverse events
- Changes observed after Baseline in formation or exacerbation of cataracts or, visual acuity. A spherical equivalent change of ≥ 0.75 diopters will be considered to be a clinically significant change regardless of changes in lens clarity.
- Occurrence of fractures after Baseline.

While AESIs may not meet the definition of an SAE, they should be reported in the same manner as SAEs (See [Section 7.1.1.9](#)). This allows them to be tracked in more detail and followed up for additional information if required. When completing the SAE form there is an extra box to check to confirm that the event is an AESI. AESIs will not be reported to the Regulatory Authorities unless they are also SUSARs.

7.1.1.6 Assessment of Adverse Event

Each AE will be assessed by the Investigator with regard to the following categories.

7.1.1.6.1 Seriousness

A serious AE (SAE) (or serious ADR or unexpected serious adverse reaction) is defined as any untoward medical occurrence that at any dose:

- Results in death
- Is life-threatening. (This means that the subject is at risk of death at the time of the event; it does not mean that the event hypothetically might have caused death if it were more severe.)
- Requires inpatient hospitalization or prolongs existing hospitalization
- Results in persistent or significant disability or incapacity
- Is a congenital anomaly or birth defect
- Is an important medical event(s) that may not be immediately life-threatening or result in death or hospitalization but that may jeopardize the subject or require intervention to prevent one of the above outcomes. Examples of such medical events include allergic bronchospasm requiring intensive treatment in an emergency room or at home, blood dyscrasias or convulsions that do not result in subject hospitalization, or the development of drug dependency or drug abuse.

Note: Cases of potential drug-induced liver injury as assessed by laboratory test values (“Hy’s Law Cases”) are also reportable. If a subject develops abnormal values in AST or ALT or both, concurrent with abnormal elevations in total bilirubin and no other known cause of liver injury, that event would be classified as a Hy’s Law Case. In this clinical study, the term SAE will be understood to also include Hy’s Law Cases.

Medical and scientific judgment should be exercised in deciding whether a case is serious and whether expedited reporting is appropriate.

7.1.1.6.2 Severity

The intensity of each PTE/AE must be assessed by the Investigator using one of the following categories, and recorded in the eCRF:

- Mild: An AE that does not interfere with usual activities
- Moderate: An AE that interferes with usual activities
- Severe: An AE that prevents usual activities

7.1.1.6.3 Causality

The Investigator will assess the causality / relationship between the study drug and the AE and record that assessment in the eCRF. Causality will be shown as Related, Possibly Related, or Not related.

7.1.1.7 Relationship to Study Procedures

Relationship (causality) to study procedures should be determined for all PTEs and AEs.

The relationship should be assessed as Yes if the Investigator considers that there is reasonable possibility that an event is due to a study procedure. Otherwise, the relationship should be assessed as No.

7.1.1.8 Collection and Reporting of AEs

7.1.1.8.1 PTE and AE Collection Period

Collection of PTEs will commence from the time the subject signs the informed consent to participate in the study and continue until the subject is first administered study medication (Day 1) or until screen failure.

Collection of AEs will commence from the time that the subject is first administered study medication (Day 1). Routine collection of AEs will continue until the Follow Up visit 21 to 28 days after the last study dose.

7.1.1.8.2 PTE and AE Reporting

At each study visit, the Investigator will assess whether any subjective AEs have occurred. A neutral question, such as “How have you been feeling since your last visit?” may be asked.

Subjects may report AEs occurring at any other time during the study. Subjects experiencing a serious PTE must be monitored until the symptoms subside and any clinically relevant changes in laboratory values have returned to baseline or there is a satisfactory explanation for the change.

Non-serious PTEs, related or unrelated to the study procedure, do not need to be followed-up for the purposes of the protocol.

All subjects experiencing AEs, whether considered associated with the use of the study medication or not, must be monitored until the symptoms subside and any clinically relevant changes in laboratory values have returned to baseline or until there is a satisfactory explanation for the changes observed. All PTEs and AEs will be documented in the PTE/AE page of the eCRF, whether or not the Investigator concludes that the event is related to the study medication. The following information will be documented for each event:

- Event term.
- Start and stop date {and time}.
- Severity.
- Investigator’s opinion of the causal relationship between the event and administration of study medication (not completed for PTEs).
- If no, provide alternative etiology or explanation.
- Investigator’s opinion of the causal relationship to study procedure(s), including the details of the suspected procedure.
- Action concerning study medication (not applicable for PTEs).
- Outcome of event.
- Seriousness.

7.1.1.9 Reporting Serious Adverse Events

All SAEs that occur during the study from the signing of the informed consent and up to 30 days after receiving the last dose of study drug, whether considered to be associated with the study drug or not, must be reported within 24 hours by email or fax to the study pharmacovigilance (PV) team. The minimum information required for an initial report is:

- Sender of report (name, address of Investigator)

- Subject identification (subject study number, initials, NOT subject name)
- Protocol number
- Description of SAE and reason why the event is categorized as serious
- Causality assessment, if possible

However, as far as possible all points on the SAE form should be covered in the initial report and the completed SAE form faxed or emailed to the pharmacovigilance team (details below). The original SAE form should be sent to the address below and the Medical Monitor and the Sponsor Chief Medical Officer informed by email. In addition, the event must be documented in the eCRF.

SAE info
Bionical Emas
[name]
[name]
[name]
Hertfordshire
[name]
United Kingdom
Email: [name] [contact]
US [contact]

After receipt of the initial report, the PV team will review the information and, if necessary, contact the Investigator, to obtain further information for assessment of the event. Bionical Emas the PV vendor will be responsible for all information processing and reporting according to local legal requirements. Where necessary, Investigators will inform the authorities in their own countries.

